3.4. Dose Adjustment/Stopping Criteria

In the SAD part, a starting dose of 2.5 mg of IFB-088 administered as oral capsule was judged to be safe for a first-in-human administration. Escalation to the next higher dose and any dose

adjustments of the next dose levels will be based on safety and tolerability results and available PK data of the previously administered dose group.

In the tentative dosing scheduled, there will be a 2-fold increase from the first dose level (2.5 mg) to the second dose level. The dose levels of the following groups will be increased by 2-fold from the previous dose level, until the dose level of 40 mg, and then 1.5-fold between the 2 last dose levels. The planned dosing schedule may be adjusted to allow administration of intermediate doses.

In the MAD part, the planned doses are 15 mg per day (2 x 7.5 mg at 12-hour interval) in cohort 1, 30 mg per day (2 x 15 mg at 12-hour interval) in cohort 2 and 50 mg per day (2 x 25 mg at 12-hour interval) in cohort 3.

The decision to proceed to the next dose level of IFB-088, will be made by the Dose Escalation Committee based on safety, tolerability and preliminary PK data obtained at the prior dose level.

Dose escalation will stop at doses, which are predicted on the basis of ongoing PK projections, to correspond to concentrations greater than the PK stopping limits (Section 3.4.2).

3.4.1. *Data Package Requirements for Dose Escalation Committee Meetings*

Dataset from a dosing session including IFB-088 plasma concentrations from the previous dose(s)/cohort(s) and safety data including AEs, vital signs, ECG (12-lead) and laboratory parameters up to at least 32 hours post last dose will be available prior to dosing the next group.

The DEC, comprised of the Investigator, the Pharmacologist of the clinical center, the statistician, a representative of the Pharmacovigilance platform, and a Sponsor's representative, will be convened prior to the start of each subsequent dosing session to interpret the clinical safety, tolerability, laboratory data and PK exposure, and make a decision to proceed to the next higher dose. Additional advisors could be invited as required.

A DEC charter will be provided to the members before the start of the study.

The DEC may unblind the treatment assignment for any subject with an SAE or for any treatment group after reasonable justification (e.g. subjects experiencing grade 3 events or findings) (Sibille et al, 2010).

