Moreover, the occurrence of moderate adverse reactions within the same system-organ-class in more than one subject, and/or clinically significant changes from baseline measurements will be considered as a safety signal and will have to lead to increase caution and a closer assessment of safety parameters in the other subjects. In such a case, data from all subjects would be to be reviewed.

3.4.3.1. *Liver Chemistry Stopping Criteria*

Liver chemistry threshold stopping criteria have been designed to ensure subject safety and to evaluate liver event etiology (in alignment with the FDA premarketing clinical liver safety guidance).

Study treatment will be stopped **for a subject** if the following liver chemistry stopping criteria is met:

- ALT or AST $\geq 3\text{xULN}$

Refer to Section 8.10, Liver Chemistry Follow-up Procedures, for details of the required assessments if a subject meets the above criteria.

3.4.3.2. *Triglycerides Stopping Criteria*

Several subjects experienced hypertriglyceridemia during the SAD part of the study. All cases were below the threshold of 5.6 mmol/L (i.e. 5 g/L), above which hypertriglyceridemia is considered clinically significant (European Atherosclerosis Society, European Society of Cardiology, French Society of Endocrinology) and no correlation or possible dose relationship was established. Moreover, some subjects with hypertriglyceridemia were in the placebo groups.

Nevertheless, a stopping criterion for triglycerides has been added in the MAD part of the study:

Study treatment will be stopped for a subject if the following criterion is met:

- Serum triglycerides ≥ 5.6 mmol/L and the subject is receiving IFB-088

Study treatment will be stopped for the whole cohort and the dose will not be escalated, if the following criterion is met:

- Serum triglycerides ≥ 5.6 mmol/L in 2 subjects receiving IFB-088.

Next cohort could be administered a lower dose intermediate between the previous cohort and the present cohort.

3.4.3.3. *Renal disorders*

The dose should not be escalated further if one of the circumstances listed below occurs **in 2 or more subjects** within the same cohort:

- Creatinine > 120 $\mu\text{mol/L}$ (1.2 ULN) (Grade 1)
- Or a change from baseline ≥ 30 $\mu\text{mol/L}$ within 24 h
- Or a change from baseline $\geq 50\%$ within one week

(KDIGO definition Ostermann and Joannidis, 2016)

- Hematuria $> 2+$, verified by cytologic exam, on 2 samples and considered at least possibly related to the IMP

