5. STUDY TREATMENT

5.1. Blinding and emergency code-break procedure

This will be a double-blind study.

One copy of the randomization list will be provided to the unblinded pharmacist for preparation of the treatment.

One set of the sealed code break envelopes will be provided to the investigational site, one for the DEC if needed, one set to the Pharmacy and one to Stragen Services, the CRO in charge of SAE processing.

The DEC will be authorized to un-blind for subjects experiencing grade 3 events or findings to help the dose escalation process (Sibille et al 2010).

The investigator or treating physician may unblind a subject's treatment assignment **only in the case of an emergency**, when knowledge of the study treatment is essential for the appropriate clinical management or welfare of the subject.

Whenever possible, the investigator will first discuss options with the sponsor **before** unblinding the subject's treatment assignment. If this is impractical, the investigator must notify the sponsor as soon as possible.

The documentation must include the name of the individual breaking the blind, the date on which the blind was broken, and a description of the event that led to the unblinding. The investigator must also indicate in source documents and in the CRF that the blind was broken and provide the date, time, and reason for breaking the blind.

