Randomization lists will be generated by *Amatsi* prior to the start of the study, using the website randomization.com, and validated by the QC team. A randomisation list will be generated for each part of the study (SAD, MAD), based on a 2-block size design by cohort. The first blocks will contain two units with a ratio of 1:1, the second block will contain six units, 1 placebo and 5 verum.

5.4.2. *Dispensing*

The study drugs will be dispensed to the investigating site by the pharmacist of the clinical site after regular prescription by the investigator or delegated medical physician and administered under investigator/medical supervision. Only subjects enrolled in the study may receive study treatment.

5.4.3. *Storage*

Study drug will be stored in a locked area, accessible only to appropriate study personnel in the pharmacy in accordance with the storage conditions defined on the IMP labels. Storage temperature will be followed by an automated reporting system.

The pharmacist on study site will be responsible for the correct storage and handling of the IMPs.

5.4.4. *Study Drug Accountability*

An accurate and current accounting of the dispensing and return of study drug for each subject will be maintained on an on-going basis by the Pharmacy.

The responsible person(s) in the Pharmacy will document the amount of study treatment produced and the amount dispensed to subjects.

All unused IMPs must be returned in the original containers. Non-used, returned study drug and empty IMP containers may be destroyed after the Pharmacist and the monitor have performed accountability and the Sponsor has confirmed in writing that destruction can be done.

Each time a dose is dispensed to a subject, the following information should be recorded: the protocol and cohort, the subject's study number, the daily dose prescribed, the number of capsules dispensed, the batch number, and the signature of the pharmacist dispensing the drugs.

As the monitor of the study must remain blinded of study treatment, a final drug accountability review and reconciliation will be completed at the completion or termination of the study, and any discrepancies must be investigated and their resolution documented.

5.4.5. *Assessment of Compliance*

All IMP doses will be administered in the clinical unit under the direct supervision of the Investigator or his designee.

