- Safety laboratory tests (hematology, coagulation, biochemistry) in fasting state, at Day 3, Day 6, Day 10 and Day 13,
- Urinalysis on Day 3, Day 6, Day 10 and Day 13,
- PK blood sampling in the morning at Day 7 pre-dose, then 1h and 2h post morning dose,
- PK urine sampling on Day 6: pre dose, 0-4h and 4-12h,
- AE monitoring.

6.5.4.4. *Day 14*

The following procedures will be performed at several time points (see Flow chart Section [3.5.3](#)):

- Study treatment dosing in 2 daily administrations separated by an interval of 12 hours,
- Vital signs (including tympanic body temperature) in the morning pre-dose,
- Diuresis monitoring,
- PK blood sampling,
- PK urine sampling,
- AE monitoring,

- Vigilance assessment at pre-dose, 1.5h post first dose and 12h post morning dose.

6.5.4.5. *Day 15 to Day 17*

The following procedures will be performed:

- Full physical exam at Day 17 before discharge,
- Vital signs every morning,
- Tympanic body temperature at Day 17,
- Safety laboratory tests (hematology, coagulation, biochemistry) in fasting state at Day 17,
- Urinalysis on Day 17,
- 12-lead ECG on Day 17,
- Diuresis monitoring on Day 15 and Day 16,
- PK blood sampling on Day 15 (17h, 19h, 21h, 24h, 30h, 36h and 42h post Day 14 morning dose) and on Day 16 (48h and 60h post Day 14 morning dose),
- PK urine sampling on Day 15 (end of collection of T12-24h and T24-36h post Day 14 morning dose) and on Day 16 (T36-48h post Day 14 morning dose),
- AE monitoring,
- Discharge after assessment of scheduled evaluations and medical authorization.

The subject will be asked to return for a follow-up visit, scheduled 7 to 14 days post last dose.

6.5.4.6. *Follow-up / End of study visit (7 to 14 days post last dose)*

The following procedures will be performed

- Vital signs measurement (including tympanic body temperature)
- Full physical examination,
- 12-lead ECG,
- Laboratory evaluation (hematology, coagulation, biochemistry and urinalysis),
- AE monitoring,
- Review of concomitant medications.

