7.2. Subject Withdrawal Criteria

Refer to Section [3.4](#) for dose adjustment/stopping criteria based on safety and PK criteria.

A subject may withdraw from study treatment at any time at his own request, or may be withdrawn at any time at the discretion of the investigator for safety, behavioral or administrative reasons.

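### Applying the individual MAD triglyceride stop in 3.4.3.2 reveals allocation to the blinded investigator, and the rule conflicts with Appendix 2; separately, 3.3 allows 24 h between MAD sub-groups where the synopsis and 3.1.2 require 36 h

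*Combined protocol and SAP*

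**What the plan says.** **Triglycerides (MAD only).** Section 3.4.3.2 stops treatment for one subject at or above 5.6 "mmol/L and the subject is receiving IFB-088". It stops the whole cohort and further escalation at or above 5.6 "mmol/L in 2 subjects receiving IFB-088". Appendix 2, which 3.4.3.5 names as the summary of the stopping rules, lists the same threshold as one subject (individual) and two subjects (cohort), with no mention of allocation. The individual stops for ALT/AST (3.4.3.1), renal findings (3.4.3.3) and QTc (3.4.3.4) do not depend on allocation either.

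**Blinding.** Under 5.1 the investigator may unblind "only in the case of an emergency". An unblinded pharmacist holds the list, and the DEC may unblind for grade 3 events or findings; 3.4.1 adds serious adverse events, or a treatment group with justification. Section 3.4.1 also sets the membership: "The DEC, comprised of the Investigator, the Pharmacologist of the clinical center, the statistician", with others. The committee "will be convened prior to the start of each subsequent dosing session". Laboratory results arrive during dosing; 6.5.4.3 schedules "Safety laboratory tests (hematology, coagulation, biochemistry) in fasting state, at Day 3, Day 6, Day 10 and Day 13".

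**Blocks.** Section 5.4.1: "The first blocks will contain two units with a ratio of 1:1, the second block will contain six units, 1 placebo and 5 verum".

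**Spacing.** The synopsis and 3.1.2 require at least 36 h between MAD sub-groups, justified as at least five half-lives. Section 3.1.2 counts from the last assessment and lets the period change on safety and PK results. Section 3.3 keeps 36 h after the first two subjects but allows at least 24 h between the two later groups of up to three.

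**The concern.** An individual stop that depends on allocation cannot be applied without someone looking up the code. No section says who does so for this rule, or how the answer is kept from the site. Even with a secure look-up, the investigator sees whether a subject at 5.6 mmol/L or more is stopped or continues, and that tells him the treatment. He also rates the causality of every adverse event (8.6.2). Safety is the primary objective, and 3.3 gives prevention of this kind of bias as the reason for the double blind.

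A site that ignores the condition is following Appendix 2 and not 3.4.3.2. The two texts give opposite instructions for a placebo subject at the threshold.

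The spacing point is separate. The last sub-group could be dosed after a shorter wait than the one the protocol justifies.

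**Working it through.** The protocol gives no operating figure for the triglyceride rule. Its one design figure (9.2: 26% chance of at least one event in 6 subjects at a 5% rate) reproduces as 1 − 0.95^6 = 0.265, but it does not bear on this point.

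**1. What one application of the individual rule discloses.** Inputs: the blocks in 5.4.1 (one active and one placebo, then five active and one placebo). Assumption: the exceedance is unrelated to treatment, so each of the 8 subjects is equally likely to have it. There are 2 × 6 = 12 possible allocations, hence 12 × 8 = 96 equally likely cases.

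| Subject at 5.6 or more | Cases | Outcome under 3.4.3.2 | What becomes known |
|---|---|---|---|
| First pair, either arm | 24/96 (2 in 8) | stop or continue | both of the pair (prior 0.50 each) |
| Second block, active | 60/96 (5 in 8) | stop | that subject, from 5/6 = 0.83 to 1.00; the other five fall from 0.83 to 4/5 = 0.80 |
| Second block, placebo | 12/96 (1 in 8) | continue | all six: he is the placebo, the other five are active |

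Under the Appendix 2 wording a stop carries no such information, and the probability of active stays at its prior of 0.50 or 0.83.

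**2. How often the rule is needed.** No SAD case reached 5.6 mmol/L (3.4.3.2), and the documents give no MAD rate. For an assumed per-subject rate p, the chance that at least one of 24 MAD subjects triggers it is 1 − (1 − p)^24:
- p = 0.5%: 1 − 0.995^24 = 0.113
- p = 1%: 1 − 0.99^24 = 0.214
- p = 2%: 1 − 0.98^24 = 0.384

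**3. Cohort rule.** If exactly two of eight subjects exceed and treatment plays no part, both are on IFB-088 in C(6,2)/C(8,2) = 15/28 of pairs. The two texts therefore disagree in 13/28 (46%) of such pairs. Two exceedances in one cohort are themselves rare: the unconditional disagreement is P(2 or more of 8) − P(2 or more of 6), which is 0.0027 − 0.0015 = 0.0012 per cohort at p = 1% and 0.0103 − 0.0057 = 0.0047 at p = 2%.

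**4. Spacing.** If 36 h is at least five half-lives, the half-life is at most 36/5 = 7.2 h. For 24 h to be five half-lives, it must be at most 24/5 = 4.8 h. At 7.2 h, 24 h is 3.3 half-lives, or 1 − 0.5^3.33 = 90% of steady state, against 1 − 0.5^5 = 97% at 36 h. At 6 h, 24 h is 4.0 half-lives. At 4.8 h or less it meets the stated reason.

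**The case against.** **The condition has a reason.** Section 3.4.3.2 reports raised triglycerides in several SAD subjects, some of them on placebo, with no dose relationship. Counting only IFB-088 subjects keeps background events from stopping a cohort. This stands for the cohort rule, where holding on any two subjects would bring back false stops. It does not justify the condition on the individual stop.

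**The rule can be operated.** A reader might infer that the stop is unworkable or leaves subjects unprotected. The documents do not support that. The pharmacist holds the list, the DEC may unblind, its charter (not seen) may set a route, Appendix 2 stops without the condition, and under 7.2 a subject "may be withdrawn at any time at the discretion of the investigator for safety, behavioral or administrative reasons". What remains is disclosure through the outcome, which none of these routes removes.

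**The disclosure is usually small.** In 5 of 8 cases it confirms what was already 83% likely. This stands; the wider disclosures are the minority.

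**The frequency is unknown.** A reader might take zero cases among the 48 planned SAD subjects as an upper bound of 1 − 0.05^(1/48) = 6.1% on the MAD rate. That assumes all 48 were measured and carries one day of dosing over to fourteen, so it bounds nothing in MAD.

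**The spacing gap may be harmless.** Waiting 36 h satisfies every section. Section 1.2.3.2 reports no accumulation at 24 h. The pre-trial prediction in Table 4 (CL/F 9.7, Vc/F 20.9) implies about 0.693 × 20.9/9.7 = 1.5 h, though that is a central-volume prediction and not an observed terminal half-life. A reader might infer that the last group would be dosed 12 h too early. That is not established, because 3.1.2 counts from the last assessment and 3.3 names no start. The inconsistency stands: 3.3 gives 24 h as a planned minimum and does not present it as a modification under 3.1.2.

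**Conclusion.** Both points hold as low-consequence corrections.

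(1) The individual triglyceride stop in 3.4.3.2 reveals allocation through its outcome, whoever looks up the code, and it contradicts Appendix 2 for a placebo subject at 5.6 mmol/L or more. One application reveals two subjects in 2 of 8 cases and six in 1 of 8; in the other 5 of 8 it moves one subject from 0.83 to 1.00. This assumes the event is unrelated to treatment. The 11% to 38% chance of needing the rule rests on assumed rates of 0.5% to 2%. The harm is to blinding and consistency; subject protection is preserved by Appendix 2 and 7.2.

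(2) Section 3.3 allows 24 h where the synopsis and 3.1.2 require 36 h. The shorter interval meets the stated five-half-life reason only at a half-life of 4.8 h or less. The documents do not give the observed value, beyond implying at most 7.2 h.

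No sample size, power or error rate is affected.

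**What to change.** (1) In 3.4.3.2, stop any individual MAD subject at 5.6 mmol/L or more regardless of allocation, as Appendix 2 and the ALT/AST, renal and QTc stops already do. Cost: an occasional placebo subject is stopped (24/96, or 1 in 4 individual stops, if the event is unrelated to treatment). Some placebo safety follow-up is lost but no PK data on the drug, and he may be replaced under 7.3.

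For the cohort rule, make 3.4.3.2 and Appendix 2 say the same thing. Whether to count all subjects, or only IFB-088 subjects as checked by unblinded DEC members without the investigator, is the sponsor's choice. The first risks stopping a cohort for background events; the second may still reveal some allocation through the decision.

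(2) In 3.3, change 24 h to 36 h, use the same start point as 3.1.2, and keep the 3.1.2 provision for modification on safety and PK results. Cost: possibly a slightly longer wait before the last sub-group.

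Both changes are amendment wording and add no assessments.

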3.5. Flow-Chart: Time and events

3.5.1. SAD part Cohort 1

Procedures	Screening (D-21 to Day -2)	Day -1	Study days																				Follow-up Day 7 to Day 14 (7 to 14 days post-last dose)
			Day 1																		Day 2		
			Pre-dose	0 h	0.16h	0.33h	0.5 h	0.75h	1 h	1.5h	2 h	2.5h	3h	4h	5h	6h	8h	12h	24h	32h			
Informed Consent	X																						
Demographics	X																						
Medical / drug and alcohol history	X																						
Psychological interview	X																						
Full Physical Exam	X																				X	X	
HIV, Hepatitis B & C serologies	X																						
Vital signs (SBP, DBP, HR) ¹	X	X	X ²				X		X		X		X	X		X	X	X	X	X	X	X	X
Tympanic temperature	X	X	X						X									X	X	X			X
Urine Drug abuse & Breath Alcohol	X	X																					
Hematology/Coagulation/Biochemistry	X	X																		X			X
Urinalysis	X	X	X															X	X	X			X
Eligibility criteria	X	X																					
Admission to Unit		X																					
Brief Physical Exam		X																					
12-lead ECG	X	X	X ³						X		X			X			X	X	X	X	X	X	X
Randomization		X																					
Study treatment dosing ⁴				X																			
Vigilance assessment			X						X									X				X	
Plasma PK Sampling			X		X	X	X	X	X	X	X	X	X	X	X	X	X	X	X	X	X	X	X
Blood sampling for exploratory biomarkers			X						X											X			
Urine PK Sampling ⁵			X																				
Adverse Event Review		X																					X
Concomitant Medication Review	X	X																					
Discharge																						X	

1	SBP, DBP and HR in supine and standing position
2	SBP, DBP and HR in triplicate with an interval of 10-30 minutes between each measurement
3	ECG in triplicate with an interval of 10-30 minutes between each measurement
4	In the first cohort one single dose fasting in the morning
5	Urine sampling for PK of IFB-088 and metabolites: pre-dose and 0-4, 4-8, 8-16, 16-32

4. STUDY POPULATION

4.1. Number of Subjects

A sufficient number of subjects will be enrolled so that 8 subjects will complete dosing and critical assessments for each of the cohorts. Six cohorts are planned in the SAD part (48 subjects) and 3 cohorts in the MAD part (24 subjects).

If a subject is withdrawn from the study, the subject may be replaced as necessary with another subject assigned to the same treatment with respect to active and placebo doses at the discretion of the sponsor's team in consultation with the investigator.

Subjects will be recruited from the clinical unit's database and via advertisements through mailing lists or announcement. The advertisement will be submitted to the Ethics Committee.

Inclusion of the same subjects in the 2 successive parts of the study (SAD then MAD) is possible, provided that the subjects have not met any discontinuation criteria during the first part, that they are not in the exclusion period (i.e. one month for SAD) and that they do not exceed the earnings for the last 12 months (*EMA Guidelines on strategies to identify and mitigate risks for first-in-human and early clinical trials with investigational medicinal products Paragraph 8.2.5*).

4.2. Eligibility Criteria

4.2.1. Inclusion Criteria

A subject will be eligible for inclusion in this study only if all of the following criteria apply:

1. Healthy male 18 to 40 years of age, inclusive, Caucasian.
2. Healthy as determined by a responsible and experienced physician, based on a medical evaluation including medical history, physical examination, laboratory tests, vital signs and ECG. A subject with a clinically significant abnormality or laboratory parameters significantly outside the reference range for the population being studied may be included only if according to the investigator's opinion, the finding is unlikely to introduce additional risk factors and will not interfere with the study procedures.
3. AST, ALT, alkaline phosphatase and bilirubin $\leq 1.5 \times \text{ULN}$ (isolated bilirubin $> 1.5 \times \text{ULN}$ is acceptable if bilirubin is fractionated and direct bilirubin $< 35\%$).
4. ECG (12 leads) normal ($120 < \text{PR} < 200$ ms; $\text{QRS} < 120$ ms; $\text{QTcF} < 450$ ms) and/or without clinically relevant impairments as judged by investigator.
5. Non-smoker, or user of tobacco- or nicotine-containing products $\leq 5/\text{day}$.
6. Negative screen for alcohol and drugs of abuse at screening and admission.
7. No history of psychiatric disorders assessed by a clinical psychological evaluation and the Mini International Neuropsychiatric Interview (MINI).

8. Body mass index (BMI) between 19 and 27 kg/m² inclusive where:

$$\text{BMI} = \frac{\text{weight in kg}}{(\text{height in meters})^2}$$

9. Subject with female partners of child-bearing potential must agree to use one of the contraception methods listed in Section 6.6.1 (Contraception requirements). This criterion must be followed from the time of the first dose of study medication until the follow up visit (for female partners) and with an additional period of 90 days (for subjects themselves).
10. Willing and able to understand and sign an approved Informed Consent Form.
11. Able to understand the protocol and to come to the visits.
12. Who is, in the judgement of the investigator likely to be compliant during the study.
13. Subject registered in the VRB file (volontaires se prêtant à des recherches impliquant la personne humaine).
14. Covered by Health Insurance System and / or in compliance with the recommendations of National Law in force relating to biomedical research.

4.2.2. *Non-selection and non-inclusion Criteria*

A subject will not be eligible for inclusion in this study if any of the following criteria apply:

1. History of asthma, anaphylaxis or anaphylactoid reactions, severe allergic responses.
2. History of relevant atopy or drug hypersensitivity.
3. Known allergy to any component of IFB-088 oral capsule or its placebo (HPMC or cellulose microcrystalline).
4. History of major medical, psychiatric illness or surgery which, in the judgment of the investigator, puts them 'at risk' or is likely to modify their handling of the study drug.
5. Acute or chronic systemic disease or disorder (respiratory, gastrointestinal, renal, hepatic, hematological, lymphatic, neurological, cardiovascular, psychiatric, musculoskeletal, genitourinary, immunological, dermatological, endocrine).
6. Impaired renal function defined by a creatinine clearance < 90 mL/min calculated using the Cockcroft-Gault equation (FDA Guidance for Industry: Pharmacokinetics in patients with Impaired Renal Function, March 2010).
7. History of nephritic colic and/or renal calculi.
8. History of drug abuse and/or regular use of tobacco- or nicotine-containing products > 5/day within three months of the study.
9. History of alcohol consumption exceeding, (on average 21 drinks/week for men) within 6 months of the first dose of study medication.

10. Drinking excessive amounts of tea, coffee, chocolate and/or beverage containing caffeine (> 4 cups / day).
11. Vital signs with a clinically significant abnormality at screening.
12. ECG with a clinically significant abnormality at screening.
13. Laboratory test values outside the clinically acceptable 'normal range' for healthy volunteers at screening.
14. Positive HIV, Hepatitis B or Hepatitis C at screening.
15. Positive urine drug test or positive breath alcohol test at screening or at admission to the clinical unit.
16. Any medication (including St John's Wort) within 14 days before administration, or within 5 times the elimination half-life of that drug, whichever is the longest (except paracetamol).
17. Treatment with an investigational drug within 30 days or 5 half-lives (whichever is longer) prior to dosing.
18. Unable to refrain from consumption of grapefruit and grapefruit juice within 7 days prior to the first dose of study medication.
19. Unwillingness to abstain from sexual intercourse with pregnant or lactating women or to use a condom and spermicide and another form of contraception (e.g., IUD, birth control pills taken by female partner, diaphragm with spermicide) if engaging in sexual intercourse with a woman who could become pregnant until discharge from the study and during 90 additional days.
20. Subjects unlikely to co-operate in the study, and/or poor compliance anticipated by the investigator.
21. Subject being in the exclusion period of a previous trial.
22. Subject having exceeded the earnings for the last 12 months, including the indemnities for the present study.
23. Subject who could not be contacted in case of emergency.
24. Subject refusing to give written informed consent.
25. Subject who has received blood or plasma derivatives in the year preceding the study.
26. Subject who has given blood within the past 3 months or have planned to give blood or sperm within the 90 days following the study.
27. Subject who has forfeited their freedom by administrative or legal award, or who is under guardianship or under limited judicial protection.

4.3. **Screen and Baseline Failures**

Data for screen and baseline failures will be collected in source documentation at the site. These data will be filled in the eCRF but will not be fully exported in the clinical database.

Only the following data will be exported and transmitted to the sponsor: reason of withdrawal, acknowledgement of consent obtainment and inclusion / non-selection / non-inclusion criteria.

